## 2.2 RATIONALE FOR CURRENT STUDY

It is unlikely that gastro intestinal absorption during a STEMI is equivalent to that of a resting patient. Hypotension and or diversion of splanchnic blood flow is likely to slow drug absorption and the intrinsic increase in platelet activity seen during STEMI (22, 23) may also inhibit the antiplatelet effect of drugs. A previous pharmacokinetic study has shown reduced drug absorption during STEMI (24). In the current study we aim to demonstrate whether prasugrel, or ticagrelor are having a significant clinical effect *during* the primary angioplasty (STEMI patients), and investigate the pharmacodynamic properties of these agents in the setting of STEMI. By also studying patients with unstable angina (UA)/NSTEMI we will investigate whether the condition of STEMI *per se* affects the pharmacodynamics of these agents.

A number of methods have been developed to assess the effect of P2Y12 receptor inhibition. Their effect is probably best measured using techniques that specifically measure P2Y12 ADP receptor activation, such as vasodilator stimulated phosphoprotein phosphorylation (VASP) and the VerifyNow P2Y12 system (Accumetrics, San Diego, CA) (24). We will utilize both of these methods in this study. We will also measure aspirin activity using the VerifyNow aspirin test.

### **3. STUDY OBJECTIVES**

- 1) To determine the degree and time-course of platelet inhibition in patients admitted with NSTEMI treated with prasugrel within the first 4 hours of loading. These data will be compared with data already collected on STEMI patients treated with prasugrel to determine whether the condition of STEMI per se reduces the efficacy of prasugrel treatment.
- 2) To demonstrate the degree and time-course of platelet inhibition by ticagrelor given acutely before emergency primary angioplasty for STEMI, during the procedure and in the following 4 hours. This will be compared with a cohort of patients presenting with NSTEMI treated with ticagrelor to determine whether the condition of STEMI per se reduces the efficacy of ticagrelor treatment.

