## 4. STUDY DESIGN

This is a pilot study which is both non-randomised and observational in nature. We plan on recruiting a total of 45 participants into the study who will comprise of patients admitted to New Cross Hospital suffering from an acute coronary syndrome. The study will complete an on-going project (REC ref no. 13/WM/0025 ethical approval granted from South Birmingham Regional Ethics Committee). Whole blood samples will be taken from participants following a single loading dose of an antiplatelet agent once the diagnosis of an ACS has been made. We anticipate the conclusion of subject recruitment in 3 months from the study start date

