### **6.2 Sampling**

**6.2.1 STEMI patients** will have a P2Y12 inhibitor administered (ticagrelor as per current local and national guidance) following verbal consent. The time of loading dose will be recorded and the patient transferred to the cardiac catheterization suite. After the insertion of the radial or femoral sheath, 15 ml of whole blood will be drawn from this sheath at 20 minutes post dosing (or as close to this time point as practicable) and also at the first balloon inflation time. A further 15 ml will be taken at 60 minutes post dosing (or as close as is practicable). Further sampling on the ward will take place after 4 hours post dosing from an antecubital vein using a 21 gauge needle (see appendix 2 for a flow chart summarizing procedure for these groups).

**6.2.2 NSTEMI patients** will have a P2Y12 inhibitor administered (prasugrel or ticagrelor) following full written consent. The time of loading dose will be carefully recorded. 15 ml of blood will be taken at 20 minutes, 60 minutes and then 4 hours post dosing solely from an antecubital vein using a 21 gauge needle (see appendix 3 for a flow chart summarizing procedure for these groups).

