### **6.3.2 VASP flow cytometry**

VASP, an intracellular actin regulatory protein, is a substrate of both cyclic adenosine monophosphate (cAMP)- and cyclic guanosine monophosphate (cGMP)-dependent protein kinases (27). Dephosphorylation of VASP follows P2Y12 stimulation. Conversely, inhibition of the P2Y12 receptor by clopidogrel and stimulation of prostaglandin E1-activated adenylyl cyclase induce phosphorylation of VASP by cAMP-dependent protein kinases. Thus levels of VASP phosphorylation/dephosphorylation reflect P2Y12 inhibition/activation.

Despite using a commercially available assay (Biocytex, Asnieres, France), VASP flow cytometry is primarily a research based assessment owing to the complexity of the procedure and the requirement for significant technical expertise. It is seen by some as a gold standard test for P2Y12 inhibition.

Whole blood transferred to tubes containing 3.2% sodium citrate is incubated with PGE1 or PGE1 and ADP for 10 minutes then fixed with paraformaldehyde, then platelets are permeabilized with non – ionic detergent. The cells are than labelled with a monoclonal antibody against 239-phosphorylated VASP and then a secondary fluoroscein isothicyanate-conjugated polyclonal antibody. Analysis will be performed on a Becton Dickinson (Plymouth, UK) FACS Calibur flow cytometer, and 10,000 platelets will be gated per assessment as per the manufacturer's instructions. Results are expressed as percentage platelet reactivity index (% PRI). VASP flow cytometry will be performed within 48 hours of sampling.

VASP Flow cytometric analysis measures activity at the P2Y12 receptor very effectively and thereby indirectly the activity of P2Y12 inhibitor and has been shown to be of value in a number of clinical trials including one carried out by our own research group (28, 29).

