### **6.3.3 Liquid chromatography with tandem mass spectrometry.**

We will be using this technique to quantify the active metabolites of prasugrel, and ticagrelor. The active metabolite of prasugrel are not stable in blood, therefore 3'-methoxy-phenacylbromide (an alkylating reagent) will be added within 30 seconds of sampling to whole blood collected in EDTA tubes to derivatize and stabilize the metabolites. Derivatized blood samples will be centrifuged at 1500g for 10 minutes. The plasma will be extracted and frozen at -80C until analysis.

Blood samples for ticagrelor active metabolite quantification will be collected in lithium heparin tubes. The active metabolites of ticagrelor are stable in blood, thus require no

stabilization. The blood samples will undergo the same processing and storage protocol as highlighted above.

The derivatized and ticagrelor plasma samples then undergo solid phase extraction and are then separated using liquid chromatography and quantified using mass spectrometry. The primary pharmacokinetic parameters (i.e. the active metabolites of prasugrel, and ticagrelor) are calculated using the maximum observed concentration ( $C_{max}$ ) and area under the plasma concentration curve (AUC). This technique has already been developed and validated used previously to detect the active metabolite of either prasugrel and ticagrelor in a number of publicized studies (30-34).

To summarize, each sample will be used for

- 1) P2Y12 inhibition estimation using the near patient Accumetrics VerifyNow test
- 2) P2Y12 inhibition will also be estimated by Flow Cytometry using VASP phosphorylation test.
- 3) Aspirin effect using near patient Accumetrics VerifyNow test.
- 4) The active metabolites of prasugrel and ticagrelor will be measured using liquid chromatography with mass spectrometry.

Time	Pre Dosing	20 Min post dosing	Balloon Time (PPCI)	60 min post dosing	4 hrs post dosing
Procedure	Consent	15 ml blood	15 ml blood	15 ml blood	15 ml blood
VN Aspirin		x	X	x	
VN P2Y12		x	X	x	X
VASP Phosphorylation		x	X	x	X
Estimation of active metabolite		x	X	x	X

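### Objective 1 compares new NSTEMI prasugrel patients with an already collected STEMI prasugrel cohort, so diagnosis cannot be separated from recruitment phase

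*Combined protocol and SAP*

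**What the plan says.** Section 3, objective 1, studies platelet inhibition over four hours in NSTEMI patients loaded with prasugrel. It then adds: "These data will be compared with data already collected on STEMI patients treated with prasugrel". The stated purpose is "to determine whether the condition of STEMI per se reduces the efficacy of prasugrel treatment". Objective 2 draws the same kind of conclusion for ticagrelor, from STEMI and NSTEMI groups that are both recruited in this study.

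Section 5.2 lists three groups of 15: Group 2 (NSTEMI, prasugrel), Group 5 (STEMI, ticagrelor) and Group 6 (NSTEMI, ticagrelor). Section 6.2.1 gives the drug for STEMI patients as "ticagrelor as per current local and national guidance".

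Section 4 describes the design: "This is a pilot study which is both non-randomised and observational in nature". On the link with the earlier data it says: "The study will complete an on-going project". The new recruitment is expected to take 3 months. The size, dates, entry criteria and sampling times of the earlier STEMI prasugrel cohort are not given.

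On the assays, section 6.3.1 describes VerifyNow as a near-patient test. Section 6.3.2 says "VASP flow cytometry will be performed within 48 hours of sampling". For the metabolite assay, section 6.3.3 says "The plasma will be extracted and frozen at -80C until analysis". Section 7 names parametric and non-parametric tests, Fisher's exact test and a logistic regression for poor outcome. It does not mention phase, batch or the earlier cohort.

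**The concern.** Every prasugrel patient with STEMI comes from the earlier phase, and every prasugrel patient with NSTEMI comes from this one. Any difference between phases in patient selection, sample handling, assay lot or surrounding care goes wholly into the STEMI minus NSTEMI difference. The study has no data with which to take it out again.

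The planned conclusion is nevertheless causal: that STEMI itself weakens the drug's effect. A phase difference could be reported as a disease effect. The protocol also words the conclusion alike for prasugrel and ticagrelor, although only the ticagrelor comparison is concurrent.

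**Working it through.** **1. The plan's own count.** 3 groups × 15 = 45, which agrees with sections 4 and 6.1. Section 6.1 has 15 patients undergoing PPCI for STEMI. These are Group 5, on ticagrelor. The number of concurrent STEMI prasugrel patients is therefore 0.

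**2. Can diagnosis and phase be separated within prasugrel?** Let μ be the mean for NSTEMI on prasugrel in the earlier phase, δ the STEMI effect and π the shift from the earlier phase to this one.

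- STEMI, earlier phase: μ + δ
- NSTEMI, this phase: μ + π
- Difference: δ − π

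The data give only δ − π. In matrix terms, a model with intercept, diagnosis and phase has rank 2 of 3. More patients do not change this, and neither does adjustment for covariates.

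**3. Do the ticagrelor groups help?** Add Groups 5 and 6, both in this phase.

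- If the STEMI effect is assumed equal for both drugs, the model has rank 4 of 4. The diagnosis estimate then has weights 0, 0, +1, −1 on STEMI prasugrel, NSTEMI prasugrel, STEMI ticagrelor and NSTEMI ticagrelor. It is simply Group 5 minus Group 6, and the prasugrel patients contribute nothing.
- If the STEMI effect may differ by drug, the model has rank 4 of 5. A STEMI effect specific to prasugrel, which is what objective 1 asks for, is still not estimable.

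**4. The assays, one by one.**

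- VerifyNow is run near the patient, and VASP within 48 hours. Samples already tested in the earlier phase cannot be re-run beside the new ones. A lot or handling difference between phases is possible; the documents do not show that one occurred.
- Metabolite plasma is frozen at −80C until analysis. Common runs are possible where plasma remains, but the protocol does not plan them.

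**5. Illustration of size.** Assumptions, none from the documents: 15 earlier STEMI patients, a two-sided 5% t-test, no true STEMI effect, and a pure phase shift stated in SD units. The standard error is √(2/15) = 0.365 SD. From the noncentral t with 28 degrees of freedom, the chance of a significant result is:

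| Phase shift | Non-centrality (shift / 0.365) | Chance of a significant result |
|---|---|---|
| 0 | 0 | 5% |
| 0.25 SD | 0.68 | 10% |
| 0.50 SD | 1.37 | 26% |
| 0.75 SD | 2.05 | 51% |
| 1.00 SD | 2.74 | 75% |

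In PRU, with an assumed SD of 80, the standard error is 80 × √(2/15) = 29.2. By the normal approximation, a shift of half a standard error (about 15 PRU) gives P(Z > 1.46) + P(Z < −2.46) = 0.072 + 0.007 = 0.079. A shift of one standard error (about 29 PRU) gives P(Z > 0.96) + P(Z < −2.96) = 0.169 + 0.002, about 17%.

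The size of the earlier cohort affects random error only. With 15 new patients, the difference detectable with 80% power is (1.960 + 0.842) × √(1/15 + 1/n): 1.14 SD for n = 10, 1.02 SD for n = 15 and 0.89 SD for n = 30. The shift π stays the same throughout.

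**The case against.** The strongest reply is that this is one project in two parts. Section 4 calls it on-going. The group numbers 2, 5 and 6 suggest the remaining cells of a larger scheme. The lay summary describes a three-drug study with the same sampling times: balloon opening, 20 minutes, 60 minutes and 4 hours. The gap may be short, and the parent protocol may fix the same entry criteria. VerifyNow is calibrated daily and quality-controlled with each batch of devices. Section 4 already declares a non-randomised, observational pilot.

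Much of this stands, and it limits what can be said. A reader might infer four stronger things that the documents do not support.

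- **That STEMI care at the site has changed.** The basis would be the remark in section 6.2.1 on ticagrelor. But Group 5 is the only STEMI group being recruited, so the remark may simply name its drug. The lay summary describes all three agents as in present use.
- **That assay batch coincides with phase for every outcome.** For VerifyNow and VASP a difference is only possible. For frozen plasma it can be avoided.
- **That section 7 pools the two phases.** It is silent on them.
- **That Group 5 against Group 6 settles the question of STEMI itself.** It removes the phase problem only. Under section 6.2, STEMI samples up to 60 minutes come from a radial or femoral sheath, and NSTEMI samples come from an antecubital vein.

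The reply does not restore the objective 1 conclusion. A short gap may make π small, but nothing in the study shows that it is. A general label of observational does not tell the reader that one comparison is concurrent and the other is not.

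**Conclusion.** The point holds in a limited form. In the prasugrel comparison, diagnosis is completely confounded with recruitment phase. This follows from the group list alone and needs no assumption. The comparison can describe a difference, but it cannot by itself attribute that difference to STEMI.

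The size of the resulting bias is unknown. The figures of 10% at 0.25 SD and 26% at 0.50 SD show how such a shift would act. They are not evidence that one exists, and they rest on an assumed 15 patients per side and assumed shifts; the PRU version also assumes an SD of 80. The length of the gap and any change in care are not documented.

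This should be corrected in the objective and in the report. It does not count against collecting the Group 2 data.

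**What to change.** 1. **Restate objective 1 and its conclusion** as a descriptive comparison with a non-concurrent STEMI cohort, and give that cohort's size and recruitment dates. Note beside it that Group 5 against Group 6 is free of the phase problem but differs in sampling site up to 60 minutes, so a claim about STEMI itself needs caution there too. Cost: wording, and a more modest prasugrel conclusion.
2. **Set a selection rule for the earlier cohort.** Include only STEMI prasugrel patients who meet the present criteria in sections 5.3 and 5.4 and the Group 2 age and weight limits in section 5.2, with samples at 20 minutes, 60 minutes and 4 hours. Allow the same leeway on timing that section 6.2.1 gives current STEMI patients, so that the earlier cohort is not held to a tighter rule. Cost: possibly a few earlier patients dropped.
3. **Use common LC-MS/MS runs.** Where earlier plasma remains at −80C, assay both prasugrel cohorts in the same runs with samples interleaved. Cost: scheduling only. This removes run differences for the metabolite outcome; it does nothing for VerifyNow or VASP.

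None of these changes needs extra patients or alters treatment.

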## 4. STUDY DESIGN

This is a pilot study which is both non-randomised and observational in nature. We plan on recruiting a total of 45 participants into the study who will comprise of patients admitted to New Cross Hospital suffering from an acute coronary syndrome. The study will complete an on-going project (REC ref no. 13/WM/0025 ethical approval granted from South Birmingham Regional Ethics Committee). Whole blood samples will be taken from participants following a single loading dose of an antiplatelet agent once the diagnosis of an ACS has been made. We anticipate the conclusion of subject recruitment in 3 months from the study start date

### 4.1 STUDY OUTCOME MEASURES

- a) Degree of platelet inhibition measured with VerifyNow™ rapid platelet function analyser
- b) Degree of platelet inhibition measured with VASP flow cytometry
- c) Concentration of prasugrel and ticagrelor active metabolite in plasma measured with liquid chromatography with tandem mass spectrometry.

This study is not powered for clinical outcomes; however clinical data will be recorded.

Clinical endpoints to be recorded for each participant will include:

- d) Angiographic variables –
  - thrombolysis in myocardial infarction (TIMI) flow at end of case,
  - slow flow/no reflow
- e) ECG variables –
  - ST-segment resolution at end of case
- f) Safety endpoints –
  - Death
  - CABG
  - TIMI major and minor bleed (see appendix 1 for bleeding criteria)

## **5. PARTICIPANT ENTRY**

### **5.1 CONSENT**

Consent will be a 2 stage process for patients undergoing PPCI for STEMI. Because the drugs given will be as per local and national recommended guidelines, consent will be verbal prior to the PPCI and first 3 blood samples. A shortened patient information sheet will be read to the patient (so as not to delay urgent treatment) and if verbal consent is gained it will be recorded in the clinical notes and the site file consent record. This is in line with NRES guidelines that suggest that patients admitted with STEMI are considered as unconscious patients initially.

Following emergency PCI when the patient is pain free and has been able to rest, a full patient information sheet will be proffered and written consent sought. If the patient does not want to be part of the trial the previous samples will be discarded and the data not used for analysis. Treatment will continue in accordance with clinical guidelines. The patients' participation in the trial will end with the 4hr sample.

For patients with UA/NSTEMI full written consent will be taken after the patient has read the full patient information sheet. Blood tests will be taken at time-points which coincide with STEMI time-points (20 minutes, 60 minutes, and 4 hours post dosage)

Patient Data will be anonymised and stored on RWHT trust fully encrypted computers

### **5.2 PRE-REGISTRATION EVALUATIONS**

All research subjects will be identified from STEMI patients admitted for PPCI at the Heart and Lung Centre in Wolverhampton and also UA/NSTEMI acute coronary syndrome patients admitted to New Cross Hospital, Wolverhampton. Patient groups (below) are carefully selected so that all patients will receive anti-platelet drugs as per current accepted National and local guidelines and as per the manufacturers' datasheets.

- 1) Group 2: Patients with NSTEMI who are under 75 years of age and greater than 60Kg in weight receiving Prasugrel loading (60mg) however: -
  - i. After sample collection patients treated with intracoronary stent placement on the same day as loading will receive prasugrel maintenance dose (10mg per day) as per licensing agreement for prasugrel
  - ii. After sample collection patients who are not stented after loading will receive clopidogrel maintenance dose (75mg per day).
- 2) Group 5: Patients admitted with STEMI receiving ticagrelor loading (180 mg) and then maintenance (90mg bd per day).

- 3) Group 6: Patients Admitted with NSTEMI receiving ticagrelor loading (180 mg) and then maintenance (90mg bd per day).

We plan to recruit 15 patients into each group.

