## 2. INTRODUCTION

### 2.1 BACKGROUND

The success of modern treatment for ST-segment elevation myocardial infarction (STEMI) is dependent, in part, on the adequate suppression of platelet activity. Primary percutaneous coronary intervention (PPCI) for STEMI management has led to marked reductions in morbidity and mortality (1). Aspirin is the mainstay anti-platelet agent (2) which acts by irreversible acetylation and inhibition of the COX-1 enzyme, thereby reducing the production of thromboxane A2, a potent platelet activator. The advent of the platelet P2Y12 inhibitors led to further improvement in outcomes in patients with acute coronary syndromes (ACS) undergoing PCI with reduced ischaemic complications (3) albeit at an increase in rate of bleeding complications. Both of these agents have a synergistic effect on platelet function with the addition of clopidogrel to aspirin leading to approximately 20% reduction in negative cardiovascular events (4). Activation of platelets leads to a conformational change in the surface glycoprotein IIb/IIIa receptor that allows cross bridging with fibrinogen and rapid aggregation (platelet thrombus formation).

During PPCI thrombus formation and dispersion can have a major impact on outcome. Intravenous platelet IIb/IIIa receptor antagonists such as abciximab were initially shown to have a positive impact on primary angioplasty outcomes leading to a class IIa indication within the European Society of Cardiology (ESC) guidelines for use in the treatment of STEMI with angioplasty (5).

As oral antiplatelet inhibition has improved (specifically with the addition of clopidogrel, prasugrel or ticagrelor) there has been a concomitant reduction in the use of intravenous IIb/IIIa agents during PCI for patients with ACS. This has been partly informed by later studies suggesting that the additive value of these agents to dual anti-platelet therapy is questionable (6). In addition, the extra bleeding complications are seen by some to be excessive (7).

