During PPCI (particularly using bivalirudin rather than i.v. IIb/IIIa antagonists) it is likely therefore that patient's would be advantaged by rapid P2Y12 antagonism. Currently there are no data concerning the comparative rapidity of clinical effect of these agents in the setting of an acute STEMI when compared to other groups.

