### **6.3 PHARMACODYNAMIC AND PHARMACOKINETIC ANALYSIS**

#### **6.3.1 VerifyNow for aspirin and P2Y12 analysis**

VerifyNow™ (Accumetrics, San Diego, California, USA) is a near patient test comprising a turbidimetric based optical detection system that measures platelet aggregation as an increase in light transmittance.

We are already using this system for clinical research in our department and it has FDA approval for the assessment of Aspirin and P2Y12 activity. VerifyNow has also been used in the assessment of ticagrelor activity in a number of studies (17, 25, 26). 2 ml of whole blood is transferred into a Greiner Bio-One Vacuette containing 3.2% sodium citrate (Accumetrics, San Diego, California, USA) and inverted carefully, after which the tube is left at room temperature for a minimum of 15 and 30 minutes for both P2Y12 and aspirin assays respectively. The tube is then loaded into a specific assay device and analysed as per the manufacturers' instructions (Accumetrics). The system is calibrated daily electronically and full quality control is performed with each batch of assay devices. This system uses a similar principle to formal platelet aggregometry. Arachidonic acid is used in the aspirin assay, ADP in the P2Y12 assay. Aspirin will already have been given in the

ambulance and its antiplatelet effect will be assessed at 20 minutes and 60 minutes after the P2Y12 inhibitor loading dose

Results are shown as aspirin response units (ARU) and P2Y12 reaction units (PRU) for aspirin and P2Y12 assays respectively.

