## 7. STATISTICS AND DATA ANALYSIS

All statistical analysis will be performed in collaboration with [name], Professor of biomedical statistics at University of Wolverhampton.

Continuous variables will be compared using parametric and non-parametric tests as appropriate. Dichotomous variables will be compared by Fishers exact test. Logistic regression analysis will be used to predict the significant independent predictors of poor outcome post angiography.

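### A IIb/IIIa antagonist given at PCI would lower VerifyNow readings and could mask a STEMI deficit, and the visible plan neither excludes, records nor handles these drugs

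*Combined protocol and SAP*

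**What the plan says.** Section 3 sets two comparisons of STEMI with NSTEMI: prasugrel (new NSTEMI Group 2 against STEMI data already collected) and ticagrelor (Group 5 against Group 6). Each asks whether STEMI in itself reduces the drug's effect.

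**The assays.** Section 6.3.1 describes VerifyNow as a "turbidimetric based optical detection system that measures platelet aggregation as an increase in light transmittance". Section 6.3.2 says of the second assay that "levels of VASP phosphorylation/dephosphorylation reflect P2Y"12 inhibition or activation. Metabolite concentration is the third measure.

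**IIb/IIIa agents.** Section 2.1 says platelet activation produces a "conformational change in the surface glycoprotein IIb/IIIa receptor that allows cross bridging with fibrinogen and rapid aggregation". It credits early results with abciximab-type drugs as "leading to a class IIa indication within the European Society of Cardiology (ESC) guidelines for use in the treatment of STEMI with angioplasty". It then reports a "concomitant reduction in the use of intravenous IIb/IIIa agents during PCI for patients with ACS", but still treats them as a current alternative: "During PPCI (particularly using bivalirudin rather than i.v. IIb/IIIa antagonists").

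**PCI.** Section 6.1 has all 15 new STEMI patients undergoing primary PCI, and section 6.2.1 samples them at first balloon inflation as well as at 20 minutes, 60 minutes and 4 hours. Section 6.2.2 samples NSTEMI patients at the last three times only, without reference to PCI. Section 5.2 mentions same-day stenting for some of Group 2 and, for the others, "After sample collection patients who are not stented after loading will receive clopidogrel maintenance dose (75mg per day". It says nothing about PCI in Group 6.

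**Analysis.** Section 7 says "Continuous variables will be compared using parametric and non-parametric tests as appropriate". Its only regression concerns poor clinical outcome, not platelet reactivity.

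**The concern.** Blocking the IIb/IIIa receptor stops the step that VerifyNow detects. A patient given such a drug would show a low P2Y12 reading even if the oral agent had not been absorbed, which is the failure the study is looking for.

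If these drugs are given more often in STEMI patients before a sample is drawn, STEMI readings fall for a reason unrelated to prasugrel or ticagrelor. The bias has one direction: a true STEMI deficit looks smaller. Without drug and PCI times, a reader could not tell whether this had happened, nor whether it explained a disagreement between VerifyNow and VASP.

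**Working it through.** **1. The plan's own figure.** 3 groups × 15 = 45, as stated in section 4. No significance level, power, effect size or standard deviation is given, so there is no power calculation to reproduce.

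**2. Mechanism.** Section 2.1 places the IIb/IIIa receptor at the step that permits aggregation. Section 6.3.1 says VerifyNow measures aggregation. Together these imply that a IIb/IIIa antagonist lowers the reading. VASP is described as intracellular phosphorylation tied to the P2Y12 receptor, and drug concentration is not a measure of aggregation, so neither is exposed in the same way.

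**3. Unequal opportunity.** All 15 Group 5 patients have PCI within the sampling period. In the NSTEMI groups the number having PCI before a given sample is not stated. If NSTEMI PCI always follows the 4-hour sample, exposure can fall only on STEMI patients and the imbalance is greatest. If it often precedes the samples with similar drug use, the imbalance shrinks.

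**4. Search for a safeguard.**
- Section 5.3 and section 5.4: no criterion on IIb/IIIa agents.
- Section 4.1: the named items are angiographic flow, ST resolution, death, CABG and bleeding; clinical data are otherwise mentioned only in general terms.
- Section 6.2: the loading-dose time is recorded; procedural drugs are not mentioned.
- Table at the end of section 6.3.3: no row for procedural drugs.
- Section 7: no adjustment, omission or sensitivity rule for platelet reactivity.

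**5. Illustrative size (assumed).** Let k of 15 otherwise average STEMI patients be exposed before a sample, and let each reading fall by a fraction f. The proportional fall in the STEMI mean is k × f / 15. With f from 0.5 to 1:

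| k | Fall in STEMI mean |
|---|---|
| 0 | none |
| 1 | 3.3% to 6.7% |
| 3 | 10% to 20% |
| 5 | 16.7% to 33.3% |

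If a proportion q of STEMI patients receive the drug, the chance of at least one exposed patient in 15 is 1 − (1 − q)^15: 54% at q = 5% and 79% at q = 10%. Both values of q are assumptions.

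**6. Leaving values in against leaving them out (assumed).** Take 15 against 15, two-sided 5%, normal approximation. The difference detectable with 80% power is (1.960 + 0.842) × √(2/15) = 1.02 SD. Suppose that is the true deficit, 3 of 15 STEMI patients are exposed, and no NSTEMI patient is.
- Values left in: the bias is (3/15) × the fall. For falls of 1, 1.5 and 2 SD the bias is 0.2, 0.3 and 0.4 SD, and power drops to 62%, 51% and 40% (58%, 45% and 32% if the added spread is counted).
- Values left out: the standard error is √(1/12 + 1/15) = 0.387 SD, and 1.02/0.387 gives power of 75%. This supposes that the remaining 12 patients are representative.

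**The case against.** The strongest reply is that exposure is not shown. No section says that any participant receives a IIb/IIIa antagonist. Section 2.1 reports falling use, doubtful added value and concern about bleeding, and says many operators now use bivalirudin routinely. This stands: use may be low or nil, and the size cannot be stated.

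Section 2.2 groups VerifyNow P2Y12 with tests specific to P2Y12 receptor activation. That fits the choice of stimulus but does not change the readout, which section 6.3.1 gives as aggregation. The manufacturer's instructions, under which the assay is run, might address interfering drugs; they are not available here. Appendices 2 and 3, the sampling flow charts, are not shown either, and the section 4.1 list is open-ended. The claim is therefore limited to the visible text.

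The study is an observational pilot without randomisation, and two of its three laboratory measures are largely protected. This limits the damage but does not remove it from VerifyNow, the first outcome listed.

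Three stronger readings should be resisted.
- A reader might infer from the column order of the section 6.3.3 table how many STEMI readings follow the balloon. The lay summary lists balloon time first, section 2.1 allows dosing only 10 to 20 minutes before PCI, and section 6.2.1 lets sample times vary. In any case, after the balloon does not mean after a IIb/IIIa drug.
- A reader might conclude that Group 2 must be restricted to patients intended for PCI. That would not address IIb/IIIa exposure, would leave Group 6 unchanged, and could slow a recruitment planned for 3 months.
- A reader might infer that the whole STEMI comparison is compromised. The mechanism reaches VerifyNow; VASP and metabolite levels are much less exposed.

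**Conclusion.** The point holds as a possible one-directional bias on VerifyNow, and the plan should be changed. If IIb/IIIa antagonists are used mainly in STEMI patients before sampling, a true STEMI deficit is understated on that outcome.

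The size is unknown. The shift of k/30 to k/15 in the STEMI mean rests on an assumed fall of half to all of each exposed reading, and is zero if nobody receives the drug. The power figures rest on assumed falls in SD units and show only that, at the same level of exposure, leaving the values out costs less than leaving them in.

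For the prasugrel objective there is a further assumption: that the earlier STEMI cohort was managed like Group 5. The documents do not describe its procedural drugs.

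**What to change.** 1. In Groups 2, 5 and 6, and from the earlier STEMI prasugrel cohort's records where available, record the PCI start time and any IIb/IIIa antagonist with its time. Mark each sample as before or after each. Record bivalirudin for description only; it is not a reason to leave a value out.

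2. Add to section 7: *VerifyNow values drawn after a IIb/IIIa antagonist are left out of the STEMI v NSTEMI comparison; the result with all values is shown as a sensitivity analysis, and VASP is shown for all patients beside it.*

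The cost is a few data fields per patient, a before/after mark per sample and a search of the earlier cohort's records, which may be incomplete. No extra blood is needed. Some VerifyNow values are lost, and not at random, because the operator chose whom to treat. That is why the all-values result and VASP in every patient stand beside the restricted comparison. The recording step alone loses no data.
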